6.4. Study Intervention/Treatment Compliance

When participants administer study intervention in the clinic (ie, at Week 1, Week 4, Week 8, and Week 12 visits), they will take the last dose from the kit dispensed at the previous visit, under medical supervision. The date and time of each dose administered in the clinic will be recorded in the source documents.

Participants will take the first dose of study intervention at home in the morning on the day following the Baseline Visit (or Day 1). When participants self-administer study intervention at home, compliance with study intervention will be assessed at each clinic visit. Compliance will be assessed by counting returned capsules during the site visits and documented in the source documents Deviation(s) from the prescribed dosage regimen should be recorded.

A record of the quantity of JZP385 or placebo capsules dispensed to and administered by each participant must be maintained and reconciled with study intervention and compliance records. Intervention start and stop dates should also be recorded.

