7. DISCONTINUATION OF STUDY INTERVENTION AND PARTICIPANT DISCONTINUATION/WITHDRAWAL

Discontinuation from study intervention does not represent withdrawal from the study (Section 7.2). Participants may discontinue from study intervention at any time for any reason, or at the discretion of the investigator. In addition, a participant may be dropped from study intervention by the investigator or sponsor for safety, behavioral, compliance and/or administrative reasons.

For participants who discontinue study intervention, all effort should be made to complete the procedures listed in the Early Discontinuation Visit (Section 1.3). Participants should be asked to return 2 weeks later for the EoS/Safety Follow-up Visit. If the Early Discontinuation Visit occurs 2 or more weeks after the last dose of study intervention, an additional safety follow-up visit is not required.

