Baseline	A blinded rater will assess TETRAS-PS (assess at same time of day as the anticipated 1-hour postdose assessment at post-baseline visits)
	[Optional] Assess items 6 and 7 of the TETRAS-PS serially across the day at 6 time points: initial assessment, 1 (use assessment from full TETRAS-PS for this time point), 2, 4, 6, and 8 hours after initial assessment
Week 4	A blinded rater will assess TETRAS-PS 1-hour postdose.
Week 8	A blinded rater will assess TETRAS-PS 1-hour postdose. [Optional] Assess items 6 and 7 of the TETRAS-PS serially across the day at 6 time points: predose, 1 (use assessment from full TETRAS-PS for this time point), 2, 4, 6, and 8 hours postdose (time points should correspond to the same time of day as Baseline assessments).
Week 12	A blinded rater will assess TETRAS-PS 1-hour postdose.
E/D Visit	A blinded rater will assess TETRAS-PS 1-hour postdose (assess at same time of day as 1-hour postdose assessment at post-baseline visits).

Abbreviations: EAC = Eligibility Adjudication Committee; ET = essential tremor; TETRAS-PS = The Essential Tremor Rating Assessment Scale - Performance Subscale.

Note: Potential participants screened an additional time (rescreened) who had previously met the inclusion criterion relative to ET diagnosis confirmed by the central EAC (Inclusion Criterion #2) will not have to complete the TETRAS-PS assessment and subsequent central review by the EAC at Screening Visit 1 or 2, as applicable.

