9.4.1.2. Intercurrent Event Strategies

Discontinuation of study intervention, as specified in Section 7.1, will be considered as intercurrent events.

For the primary and key secondary estimands, the following 2 types of intercurrent events will be considered:

- Discontinuation of treatment due to an AE, for lack of efficacy, or any other reason. Participants who experience this type of intercurrent event will be treated as if they did not experience an intercurrent event (hypothetical strategy). The hypothetical strategy used is defined as the pharmacologic effect of JZP385 compared to placebo assuming the intercurrent event did not happen with continuation of study intervention for the duration of the study. Analyses will be conducted using data collected at time points obtained at or prior to participants' discontinuation of study intervention and combined with imputed values for post-discontinuation time points for which the underlying assumptions are considered appropriate.
- Any change to concomitant antitremor medication use after the initiation of study intervention, including but not limited to the following: 1) starting a new antitremor medication, 2) stopping a concomitant antitremor medication, and 3) a dose or regimen change to current antitremor medication. This type of intercurrent event will be disregarded, and measurements obtained subsequently will be reported and analyzed (treatment policy). Treatment policy is defined as the effect of randomized treatment over the study period regardless of the occurrence of the intercurrent event. In accordance with treatment policy, data collected after this type of intercurrent event will be reported and included in analyses.

If a participant experiences a combination of both types of ICE (eg, change the use of anti-tremor medication and discontinue the study intervention afterwards), each ICE should be treated

independently. Data collected after the change of antitremor medication but on or before the study intervention discontinuation will be included in analyses per treatment policy, the postdiscontinuation data will be handled by hypothetical strategy.

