4.2. Study Estimands and Endpoints

4.2.1. Primary Estimand

The primary estimand of the study is defined as:

- Treatment: 10, 20, and 30 mg/day JZP385 and placebo.
- Population: Adults with moderate to severe ET.
- Variable: Change from Baseline to Week 12 on the TETRAS composite outcome score*.
- Intercurrent events:
 - o Discontinuation of treatment due to an AE, for lack of efficacy, or any other reason. Participants who experience any intercurrent event will be included as if they did not experience the intercurrent event (hypothetical strategy).

- O Any change to concomitant anti-tremor medication use after the initiation of study intervention, including but not limited to the following: 1) starting a new antitremor medication, 2) stopping a concomitant antitremor medication, and 3) a dose or regimen change to current antitremor medication. This type of intercurrent event will be disregarded, and measurements obtained subsequently will be reported and analyzed (treatment policy).⁺
- Summary: Difference in the mean TETRAS composite outcome score from Baseline to Week 12 between each dose of JZP385 and placebo.
- * The TETRAS composite outcome score is the sum of modified items 1 to 11 of the TETRAS-ADL subscale and modified items 6 and 7 of the TETRAS-PS. For TETRAS-ADL, each item is modified from 5 response items to 4 response items by collapsing options 0 and 1 together and for TETRAS-PS, each item is modified from 9 response items (due to 0.5 scoring increments) to 4 response items. As such, the range of possible scores at each visit is 0 to 42.
- + A blinded review of all concomitant medications and therapies will be performed prior to database lock to determine the occurrence of this intercurrent event.

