7.2.3. Visit Windows

All scheduled, unscheduled, and early termination assessments will be summarized by derived analysis visit per the Table 5, regardless of whether the visit was performed on-site or remotely. Visit dates will be mapped based on the scheduled Period of each visit, with adjusted analysis-defined visit windows as specified in Table 5.

Table 5 Visit Windows for Assessments or Measurements

Study Period	Scheduled Visit	Scheduled Study Day	TETRAS-ADL, TETRAS-PS, CGIs	CGIc and PGIc	QUEST, SF-36v2, ETEA	C-SSRS ^b , Clinical Laboratory ^{c, e} , Urinalysis ^e , Weight, Vital Signs, Breath Alcohol ^{d, e} , ECG, Urine Pregnancy test
Screening	Visit 1/Visit 2 ^a	-49 to -8	Any Day up to -2	na	n/a	Any Day up to -2
Baseline ^f	Baseline Visit	-1	Closest prior to dosing	na	Closest prior to dosing	Closest prior to dosing
	Week 1	7 (-1, +2)	na	na	na	2 - 14
Double-Blind	Week 4	28±3	2 - 42	2 - 42	na	15 - 42
Treatment	Week 8	56± 3	43 - 70	43 - 70	na	43 - 70
	Week 12	84± 3	71 - 98	71 – 98	2 - max	71 - max
Safety Follow-up	End of Study	98± 3	na	na	2 - max	2 – max ^f

^a Screening Visit 2 is only for participants who need to wash out of any medications that impact tremor (e.g., anti-tremor medications) prior to Baseline;

^b At screening visit 1, C-SSRS screening/baseline version, at screening visit 2, C-SSRS since last visit version;

^c Clinical laboratory includes hematology and chemistry labs;

^dBreath Alcohol is not collected at W1;

^e Not collected at Safety Follow-up.

^f For participants who randomized without taking the study intervention, the Baseline Visit or latest Screening Visit (if Baseline Visit is not available) will be mapped.

If multiple assessments or measurements are recorded within a single visit window (including scheduled, unscheduled, repeated, and retest assessments or measurements as well as early discontinuation data), the following rules will be applied to determine the result from which assessment will be used for the summaries for that analysis visit.

- The priority will always be given to the scheduled visit within the corresponding visit window (e.g., scheduled W4 visit corresponds to Week 4 visit window) regardless of the relative distance to the scheduled Visit Day.
- If there are 2 or more observations within the same visit window, then the non-missing one closest to the scheduled Visit Day will be used in the analysis.

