7.6. Changes to Planned Analyses

Section 9.4.1.4 of the Protocol outlines the approach to imputation of missing item scores, as part of the TETRAS composite outcome score. Based on these rules, it was possible for a participant to have a missing TETRAS PS score at a visit and still have a valid composite outcome score. The rules have been amended to change the imputation of missing item scores to be managed within the individual subscale scores (ADL or PS) before the composite outcome score is calculated. The details of the new calculation are specified in Section 7.2.5.

The mITT Analysis Set defined in the Protocol Section 9.3 has been updated to ITT, to include all randomized participants for the primary efficacy analyses.

For Adverse Events of Special Interests defined in Protocol Section 8.4.6, presyncope was removed in the formal definition of AEOSI in Section 10.2.1.

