9.1.2. Primary Analyses

For the main analysis of the primary efficacy endpoint, a MMRM will be used to include the change in the TETRAS composite outcome score from Baseline to Weeks 4, 8, and 12.

$$dTCOM_{ij} = \alpha_i + \beta_1 * baseTCOM_i + \beta_2 * week_j + \beta_3 * treatment_i + \beta_4 * treatment_i * week_j + \beta_5 * baseTCOM_i * week_i + \beta_6 * stratum_i + \varepsilon_{ij}$$

The model will include treatment group ($treatment_i$), baseline TETRAS composite outcome score ($baseTCOM_i$), week (as a discrete factor, $week_j$), treatment group by week interaction ($treatment_k * week_j$), week by baseline interaction ($week_j * baseTCOM_i$), and randomization

stratum ($stratum_i$) as fixed effects, and week repeated within each participant as a repeated effect (α_i). For the purposes of this model, "week" refers to the treatment visit, as determined using the windows specified in Section 7.2.3. An unstructured variance-covariance matrix will be used to model the correlation among repeated measurements. If the model fails to converge on the Newton-Raphson Algorithm, the alternative Fisher scoring algorithm should be explored before considering other variance-covariance structures. Kenward-Roger's degrees of freedom will be used.

Least squares mean and standard error for Week 12 will be provided for each treatment group. The difference between the LS means of JZP385 and placebo for Week 12, along with the SE of the difference, 95% CI and associated p-value corresponding to testing the hypothesis of no difference between the treatment groups will also be provided.

The assumption of normality will be examined by obtaining a histogram and a QQ-plot on studentized residuals. Based on these plots, if there exists evidence to suggest the departure from the normality assumption, a non-parametric MMRM with the covariate and response variables replaced by their ranks will be used for the primary analysis.

The following is an example of SAS code for linear mixed model analysis:

PROC MIXED;

CLASS PATIENT TRT WEEK STRATUM;

MODEL CHG = BASELINE TRT WEEK STRATUM TRT*WEEK BASELINE*WEEK /

RESIDUAL OUTP=RESIDUAL DDFM=KR;

REPEATED WEEK/TYPE=UN SUB=PATIENT;

LSMEANS TRT*WEEK / CL DIFF ALPHA=0.05;

RUN;

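### SAP 7.2.3 has no last-dose cut-off, so early-discontinuation scores taken off drug can enter the primary and CGI-S analyses, which Protocol 9.4.1.2 limits to data up to discontinuation

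*SAP*

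**What the plan says.** Protocol 9.4.1.2 handles discontinuation of study drug by a hypothetical strategy in the primary and key secondary estimands, and gives a data rule: "Analyses will be conducted using data collected at time points obtained at or prior to participants' discontinuation of study intervention", with values after that point imputed. For a participant who changes antitremor medication and later stops study drug, it again keeps data only up to the stop.

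SAP 4.2.1 and 4.2.2 name the hypothetical strategy but give no rule for excluding data. SAP 7.2.3 builds the analysis visits: "All scheduled, unscheduled, and early termination assessments will be summarized by derived analysis visit per the Table 5". For TETRAS and CGI-S, Days 2-42 become Week 4, Days 43-70 Week 8 and Days 71-98 Week 12. Early-discontinuation data compete within a window; a scheduled visit has priority, and otherwise the observation nearest the target day is used. Days since last dose play no part. In SAP 9.1.2 the week factor of the MMRM "refers to the treatment visit, as determined using the windows specified in Section 7.2.3".

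The Schedule of Activities places TETRAS-ADL, TETRAS-PS and CGI-S at the Early Discontinuation (E/D) visit. Protocol 7 foresees that this visit may be late: "If the Early Discontinuation Visit occurs 2 or more weeks after the last dose of study intervention", no further safety visit is needed. On-site dosing is scheduled only at Weeks 1, 4, 8 and 12 (Schedule of Activities; Protocol 6.4).

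**The concern.** As written, the dataset rule admits scores that the estimand's data rule excludes. An off-drug score would be analysed as an observed value in the primary MMRM and the CGI-S analysis, and would carry into their imputation-based versions. A participant with on-drug Week 4 and Week 8 scores who stops and then has an off-drug E/D score on Days 71-98 would also pass as a completer under SAP 9.1.4.

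The estimate would then not be the declared one. If the effect fades off drug, the bias is toward no difference, so the cost is power and not false positives. Power matters here because the fixed sequence in SAP 7.4 starts with 30 mg on the composite score and stops at the first failure; a loss at step 1 closes the five later tests. Without a stated cut-off, two programmers could also build different primary datasets in good faith.

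**Working it through.** **Inputs from the documents** (Protocol 9.2, SAP 5.3): 80 evaluable per arm, difference 3.1, SD 6.0, two-sided 0.05, t-test; CGI-S responders 66% versus 40%, chi-square test; 20% dropout, 400 randomized. Windows are from SAP 7.2.3, Table 5.

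**Assumptions** (not in the documents): 20% stop drug in every arm, spread evenly over Days 1-83; late E/D visits fall 14 days after the last dose; effect 3.1 at all three visits; correlation between visits 0.5-0.7.

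**1. The plan's own figures.** Noncentrality = 3.1 / (6 × √(2/80)) = 3.1 / 0.949 = 3.27 on 158 df, giving power 90.1%. CGI-S by pooled chi-square: 91.7%. Inflation: 80 / (1 − 0.20) = 100 per arm. All agree with the plan.

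**2. One participant traced.** Last dose Day 60, E/D visit Day 75: the score is 15 days off drug. Day 75 lies in the Week 12 window and no scheduled Week 12 visit exists, so the score becomes the observed Week 12 value. Protocol 9.4.1.2 would exclude it and impute.

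**3. Does a later SAP step remove it?** SAP 9.2.2 imputes missing CGI-S values; this one is not missing. The control-based step in SAP 9.1.3.1 resets only values that were themselves imputed. SAP 7.6 lists three changes from the protocol: item imputation, mITT to ITT, and the removal of presyncope. This is not among them.

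**4. Count if every E/D visit is 14 days late.** Stop days 1-27 give an off-drug Week 4 score, 29-55 an off-drug Week 8 score and 57-83 an off-drug Week 12 score. Stop days 28 and 56 are displaced by the scheduled visit. Each group is 27/83 = 32.5% of the 80 stoppers, or 26, and 78 in all. Week 12 then has 320 + 26 = 346 values, or 86.5 per arm.

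**5. Effect on the Week 12 difference.** Counting only the Week 12 scores, 26/346 = 7.5% carry no effect, so 3.1 × (1 − 0.075) = 2.87 if all effect is lost. The MMRM falls further, because off-drug Week 4 and Week 8 scores also inform the missing Week 12 values. A large-sample simulation of the unstructured MMRM (200,000 per arm, simulation error about 0.02) gives:

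| E/D visits | Effect lost | Difference | Power, 80 per arm | Power, 86.5 per arm |
|---|---|---|---|---|
| On the day of stopping | none | 3.08-3.12 | about 90% | – |
| A quarter 14 days late | all | 2.99-3.01 | 88.0-88.4% | – |
| All 14 days late | half | 2.85-2.88 | 85-86% | 87.4-88.1% |
| All 14 days late | all | 2.64-2.69 | 79-81% | 82.1-83.4% |
| All 14 days late, off-drug scores removed | – | 3.09-3.10 | about 90% | – |

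The 86.5 column is the fairer one for the all-late rows, since the off-drug scores add to the 80. With stopping concentrated early, the all-late, all-lost difference is 2.70-2.78.

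**6. CGI-S.** A similar simulation with predictive mean matching turns the planned 26 points into 25.1-25.2 if a quarter are late and all effect is lost (power 90% versus 91.7%), and into 22.4-23.0 if all are late and all effect is lost (82-84%, at 80 per arm).

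**The case against.** The best defence is that the SAP should be read as a whole. SAP 9.2.2 sends treatment dropouts, as well as missing observations, to multiple imputation. SAP 9.1.3.1 speaks of imputed values after discontinuation. SAP 9.2.6.3 and 9.2.6.4 waive imputation of post-event data for QUEST and ETEA, which makes most sense if such data are imputed elsewhere. SAP 7.2.3 is a general mapping section that also serves laboratory and ECG data, and SAP 7.6 declares no departure from Protocol 9.4.1.2. On conduct, Protocol 7.2 ties the E/D visit to the time of leaving the study, and Protocol Table 5 asks for TETRAS-PS one hour after a dose.

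Much of this stands. The intent is clear, and a score taken at the time of stopping complies with the protocol. A reader might infer that the SAP has moved to a treatment-policy analysis of discontinuation; the documents do not support that. A reader might also infer that every early-termination score contaminates the analysis; that fails too, because only Days 2-98 map, scheduled visits displace E/D scores, and timely E/D scores are legitimate.

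What does not stand is that intent is enough. None of these passages sets an observed off-drug score to missing, while the one section that builds the dataset expressly includes early-termination data. The one-hour-postdose instruction cannot be met by someone who has already stopped, a case Protocol 7 foresees.

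**Conclusion.** The gap is real: the SAP's visit rule does not carry out the data restriction in Protocol 9.4.1.2. It is an omitted step and not a chosen change of estimand, and it should be corrected.

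Its size cannot be settled from the documents, which give neither E/D lag nor rate of offset. The range runs from no dilution with timely visits, through about 3.0 points and 88% power when a quarter are late and all effect is lost, to 2.64-2.69 points when all are late and all effect is lost. A reader might take the last case as the expected loss. Nothing in the documents supports every visit being two weeks late; the Protocol 7 clause only waives a redundant safety visit and gives no frequency. The direction is also conditional: the bias is toward no difference if the effect fades off drug.

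**What to change.** Add to SAP 7.2.3 that, before windowing, TETRAS and CGI-S scores taken after permanent discontinuation are set to missing for the primary and key secondary hypothetical-strategy analyses and for their imputation, control-based, tipping-point and completers versions. Define the cut-off as the last-dose date in SAP 7.2.2 plus a pre-specified grace period. Justify that period pharmacokinetically: Protocol 4.3 gives 5 days to steady state and Protocol 2.2 describes two active metabolites, so once-daily dosing alone is a weak argument for a 1-day limit. Do not flag temporary interruptions, keep the removed scores in listings, and settle the rule before unblinding.

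The change needs no new visits, data or participants. Its cost is some observed values. With even stopping and every visit 14 days late, 26 of 346 Week 12 values go, leaving 320 (80 per arm, the planned evaluable number). About 26 participants who stop before Day 28 would have no post-baseline score, or about 43 if stopping is concentrated early. Reliance on the missing-at-random assumption rises slightly.

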10.3. Laboratory Assessments

The continuous clinical laboratory assessments (hematology, chemistry, and urinalysis) will be summarized at each visit using descriptive statistics. The change from Baseline will be provided at the Week 12.

Shift tables will summarize changes in clinical laboratory assessments at each of the post-baseline visit with respect to baseline. Lab values are categorized into L1, low, normal, high, or H1 based on the lab reference range. L1 and H1 values are predefined per the lab vendor alert ranges and correspond to the extreme abnormal lower and higher ranges, respectively.

Abnormal laboratory assessments deemed clinically significant by the investigator will be reported as an adverse event.

A listing of Participants with abnormal value(s) according to the following criteria will be summarized using Safety Analysis Set:

- Any laboratory value that falls into the pre-defined low or high panic ranges (L1 or H1) per the Q2 Laboratory Range Chart.
- Alanine aminotransferase (ALT) or aspartate aminotransferase (AST) \geq 3 × Upper Limit of Normal (ULN) and total bilirubin \geq 2 × ULN, inclusive (Hy's Law).
- AST or ALT \geq 5 × ULN,

- Creatinine $> 1.5 \times ULN$
- Participants positive for alcohol, urine drug screen or pregnancy assessments

All laboratory results, including pregnancy test, drug screen, and alcohol screen, will also be presented in subject data listings.

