10.4. Vital Signs

The following vital signs measurements will be reported for this study.

- Supine and standing systolic blood pressure (SBP), (millimeter of mercury [mmHg])
- Supine and standing diastolic blood pressure (DBP) (mmHg)
- Supine and standing pulse rate (beats per minutes [bpm])
- Sitting or supine respiratory rate (breaths/min)
- Body Temperature (°C)
- Weight (kg)
- Height (cm)
- BMI (kg/m2) [derived]

The orthostatic vital signs will be derived as the difference found by subtracting the supine measurement from the standing measurements. The orthostatic measurement will be summarized with the supine and standard measurements.

These vital signs (with the exception of the BMI which will be calculated programmatically) will be measured during the screening visit and each in-clinic scheduled visit. Height (cm) will be obtained at screening visit only.

The following summaries will be provided for vital signs data:

Jazz Pharmaceuticals

Statistical Analysis Plan - Protocol JZP385-201

- Observed and change from baseline by visit
- Incidence of markedly abnormal criteria by visit

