10.5.1. ECG Abnormal Criteria

Abnormal quantitative ECG measurements will be identified in accordance with the following predefined markedly abnormal criteria:

Observed values for QT interval, QTcB interval and QTcF will be classified as follows at each time point:

- > 450 msec
- > 480 msec
- > 500 msec

Change from baseline for OT interval, OTcB interval and OTcF will be classified as follows:

- >30 msec increase from baseline
- >60 msec increase from baseline

A listing of participants meeting markedly abnormal criteria as well as a listing of participants with abnormal ECG overall assessment will also be provided based on the Safety Analysis Set.

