10.6. Other Safety Endpoints

10.6.1. Columbia-Suicide Severity Rating Scale

The Screening/Baseline version of the C-SSRS will be administered to participants at screening visit.

The Since Last Visit version of the C-SSRS will be administered to participants at every scheduled in-clinic after the screening visit 2 up to the Safety Follow-up visit or early discontinuation visit.

The following summaries will be provided for the C-SSRS data by visit and by treatment group:

- Number and percentage of participants with any suicidal ideation (i.e., having responded yes to any of the 5 types of suicide ideation) as well as broken down by type of suicidal ideation
- Number and percentage of participants with any suicidal behavior (i.e., having responded yes to any of the 4 or 5 types of suicidal behavior, as applicable) as well as broken down by type of suicidal behavior
- Number and percentage of participants with any suicidal behavior or any suicidal ideation;
 a subject having reported both suicidal behavior and suicidal ideation will be counted only once
- Number and percentage of participants with self-injurious behavior without suicidal intent

Missing data will not be imputed. All C-SSRS parameters will be presented in the subject data listing.

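### SAP 7.2.3 keeps one safety result per window and always prefers the scheduled visit, so some early-discontinuation and unscheduled results never reach the by-arm outlier tables

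*SAP*

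**What the plan says.** SAP 7.2.3 maps all scheduled, unscheduled and early-termination assessments to analysis visits through Table 5. The last column of that table holds the safety measures, from C-SSRS and clinical laboratory through to "ECG, Urine Pregnancy test". Where a window holds several results, expressly including unscheduled, repeat and early-discontinuation data, "the following rules will be applied to determine the result from which assessment will be used for the summaries for that analysis visit". The order is:

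- First, "The priority will always be given to the scheduled visit within the corresponding visit window", whatever its distance from the scheduled day.
- Otherwise, "then the non-missing one closest to the scheduled Visit Day will be used in the analysis".
- Ties go to the earliest result.

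Listings keep every record by nominal visit.

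The by-arm outputs for unusual values are these:

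- Vital signs (SAP 10.4): "Incidence of markedly abnormal criteria by visit".
- ECG (SAP 10.5.1): "Observed values for QT interval, QTcB interval and QTcF will be classified as follows at each time point".
- C-SSRS (SAP 10.6.1): "The following summaries will be provided for the C-SSRS data by visit and by treatment group".
- Laboratory (SAP 10.3): "Shift tables will summarize changes in clinical laboratory assessments at each of the post-baseline visit with respect to baseline".

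None of these sections specifies a by-arm table of the worst or any post-baseline value.

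**The concern.** A rule that picks one value per window suits by-visit means. For outlier incidence it can discard the value of interest. Suppose a participant has an unremarkable Week 4 visit on Day 28 and stops for intolerance, with an E/D visit on Day 35. Both results fall in the Day 15 to 42 window, the Week 4 result is used, and the E/D vital signs, ECG, laboratory results and C-SSRS leave the by-visit tables. An ECG repeated because the investigator was worried is treated the same way.

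Two features of the design add weight. Under Protocol 4.1 and 6.5, a participant who cannot tolerate the assigned dose must stop, so the E/D visit is where intolerance is measured. Also, the nominal Week 1 visit (Day 7) is the last day at the starting dose in the active arms, while its window runs to Day 14. An E/D result from Days 8 to 14, after the first dose step, can thus be replaced by one taken before that step.

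At stake is the descriptive safety comparison between arms, which serves a secondary objective in a trial with no data monitoring committee.

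**Working it through.** **Inputs**

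- Safety windows (SAP Table 5): Week 1, Days 2–14; Week 4, Days 15–42; Week 8, Days 43–70; Week 12, Day 71 onward.
- Scheduled days (same table): 7 (−1, +2), 28 ± 3, 56 ± 3 and 84 ± 3.
- Dropout (SAP 5.3): 20%, with 80 evaluable per arm.

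**The plan's own figure.** 80 / (1 − 0.20) = 100 per arm and 4 × 100 = 400 in total, as stated. Expected dropouts are 100 − 80 = 20 per arm.

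**Rule applied.** An E/D result on day *d* is superseded when the scheduled visit of its window has already taken place. An E/D visit before that point supplies the window's value and is kept. The count assumes that earlier scheduled visits were attended and gave non-missing results.

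**Nominal visit days, E/D on any day from 2 to 84 (83 days)**

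- Days 8–14: 7
- Days 29–42: 14
- Days 57–70: 14
- Total: 35; 35 / 83 = 42%
- Per arm: 0.42 × 20 = about 8, if all 20 dropouts attend an E/D visit at evenly spread times

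**Sensitivity to timing**

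| E/D days | Visits at late edge (9, 31, 59, 87) | Nominal | Visits at early edge (6, 25, 53, 81) |
|---|---|---|---|
| Even over 2–84 | 27/83 = 33% | 35/83 = 42% | 45/83 = 54% |
| All within 2–28 | 5/27 = 19% | 7/27 = 26% | 11/27 = 41% |

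The range over these scenarios is about 19% to 54%. The top figure counts Days 82–84, after a Week 12 visit on Day 81, when an E/D visit is unlikely; without them it is 42/80 = 53%. If every discontinuation came after Day 28, the nominal share would be 28/56 = 50% (39% to 61%). The documents give no discontinuation times, so no row is preferred.

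**Unscheduled results.** Any unscheduled result in a window that also holds a non-missing scheduled result is superseded, whatever its day.

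**The case against.** The case against has several parts, and most of it stands as a limit on scope.

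- **Nothing is deleted.** A reader might infer that the data are lost. They are not: all records are listed.
- **Some any-time capture exists.** A reader might infer that every safety output is tied to a visit. SAP 10.3 also plans an output for any panic-range laboratory value, Hy's Law cases, AST or ALT at 5 × ULN or more, and creatinine above 1.5 × ULN, none of it tied to a visit. It is described as a listing, so by-arm counts are not assured. In SAP 10.5.1 the QT/QTc change categories (>30 and >60 msec) name no time point. Protocol 9.4.5 promises the number and percent of participants beyond QT thresholds without restricting this to visits, and SAP 7.6 does not withdraw it. An any-time reading is therefore open for ECG, but the SAP does not state it.
- **The End of Study row.** Its window for C-SSRS, vital signs, weight and ECG is Day 2 onward. Under Protocol 7, no follow-up visit is needed when the E/D visit comes 2 or more weeks after the last dose, and that E/D result may then fill the row. The SAP does not say so, and laboratory tests are not collected there.
- **Adverse-event tables.** Abnormalities judged clinically significant are recorded as adverse events (Protocol 8.3.4 and Appendix 4; SAP 10.3), as is active suicidal ideation or behavior (Protocol 8.3.6). The treatment-emergent tables count these by arm regardless of visit window.
- **Direction of bias.** The Schedule of Activities shows no on-site dose at the E/D visit, which may fall well after the last dose, and Protocol 4.3 puts steady state at 5 days. Some E/D values may reflect little remaining drug.

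What these points do not supply is a by-arm incidence, over all post-baseline results, for markedly abnormal vital signs, observed QT/QTc categories, C-SSRS categories or laboratory shifts.

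**Conclusion.** The point holds in a bounded form. As written, the SAP leaves superseded E/D and unscheduled results out of the four sets of by-visit outlier tables, and no by-arm table restores them. What is mainly lost is by-arm incidence of threshold crossings that were not reported as adverse events.

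The size is 42% of possible E/D days at nominal timing, or about 8 of 20 per arm, with about 19% to 54% under even or early discontinuation. The per-arm count rests on full E/D attendance, which participants lost to follow-up will not meet, and the 20% is dropout from all causes, not intolerance alone. Counting only from Day 8 would give 35/77 = 45%, but that omits Days 2–7, when nothing is superseded at nominal timing. In most scenarios more than half of E/D results are kept.

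A reader might infer that the safety comparison is biased toward no difference. The documents do not establish that. Outlier incidence would be understated in arms with more discontinuations if E/D values are more often abnormal than the scheduled values that replace them. That is plausible, but neither the dropout pattern by arm nor the distribution of E/D values is given. The omission itself does not depend on it. Efficacy conclusions are unaffected, and the safety analyses are descriptive.

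**What to change.** Keep the Table 5 selection rule for by-visit summaries. Add to SAP 7.2.3, 10.3, 10.4, 10.5.1 and 10.6.1 an any-post-baseline (worst value) row by arm for:

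- markedly abnormal vital signs;
- QT/QTc observed and change categories;
- C-SSRS ideation and behavior;
- laboratory shifts.

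The row should use all scheduled, unscheduled, repeat and E/D results from first dose to 14 days after last dose, which matches the treatment-emergent period in SAP 10.2. It sits beside the by-visit tables and need not replace them. It would also settle whether the >30 and >60 msec categories are meant per visit or at any time.

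The cost is SAP wording and slightly more programming, with no new data. Some outlier percentages will rise. If the SAP is not reopened, SAP section 3 already allows additional analyses to be documented with a rationale in the clinical study report.
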